9.4.3. Other Analyses

No other analyses will be conducted for this study.

10. STUDY GOVERNANCE CONSIDERATIONS

10.1. Posting of Information on Publicly Available Clinical Trial Registers

Study information from this protocol will be posted on publicly available clinical trial registers before enrollment of subjects begins.

10.2. Regulatory and Ethical Considerations, Including the Informed Consent Process

Prior to initiation of a site, GSK will obtain favourable opinion/approval from the appropriate regulatory agency to conduct the study in accordance with International Conference on Harmonization (ICH) Good Clinical Practice (GCP) and applicable country-specific regulatory requirements.

The study will be conducted in accordance with all applicable regulatory requirements, and with GSK policy.

The study will also be conducted in accordance with ICH GCP, all applicable subject privacy requirements, and the guiding principles of the current version of the Declaration of Helsinki. This includes, but is not limited to, the following:

- IRB/IEC review and favorable opinion/approval of the study protocol and amendments as applicable
- Investigator reporting requirements (e.g. reporting of AEs/SAEs/protocol deviations to IRB/IEC)
- GSK will provide full details of the above procedures, either verbally, in writing, or both.
- Signed informed consent must be obtained for each subject prior to participation in the study

- The IEC/IRB, and where applicable the regulatory authority, approve the clinical protocol and all optional assessments, including genetic research.
- Optional assessments (including those in a separate protocol and/or under separate informed consent) and the clinical protocol should be concurrently submitted for approval unless regulation requires separate submission.
- Approval of the optional assessments may occur after approval is granted for the clinical protocol where required by regulatory authorities. In this situation, written approval of the clinical protocol should state that approval of optional assessments is being deferred and the study, with the exception of the optional assessments, can be initiated.

10.3. Quality Control (Study Monitoring)

- In accordance with applicable regulations including GCP, and GSK procedures, GSK monitors will contact the site prior to the start of the study to review with the site staff the protocol, study requirements, and their responsibilities to satisfy regulatory, ethical, and GSK requirements.
- When reviewing data collection procedures, the discussion will also include identification, agreement and documentation of data items for which the eCRF will serve as the source document.

GSK will monitor the study and site activity to verify that the:

- Data are authentic, accurate, and complete.
- Safety and rights of subjects are being protected.
- Study is conducted in accordance with the currently approved protocol and any other study agreements, GCP, and all applicable regulatory requirements.

The investigator and the head of the medical institution (where applicable) agrees to allow the monitor direct access to all relevant documents

10.4. Quality Assurance

- To ensure compliance with GCP and all applicable regulatory requirements, GSK may conduct a quality assurance assessment and/or audit of the site records, and the regulatory agencies may conduct a regulatory inspection at any time during or after completion of the study.
- In the event of an assessment, audit or inspection, the investigator (and institution) must agree to grant the advisor(s), auditor(s) and inspector(s) direct access to all relevant documents and to allocate their time and the time of their staff to discuss the conduct of the study, any findings/relevant issues and to implement any corrective and/or preventative actions to address any findings/issues identified.

10.5. Study and Site Closure

- Upon completion or premature discontinuation of the study, the GSK monitor will conduct site closure activities with the investigator or site staff, as appropriate, in

accordance with applicable regulations including GCP, and GSK Standard Operating Procedures.

- GSK reserves the right to temporarily suspend or prematurely discontinue this study at any time for reasons including, but not limited to, safety or ethical issues or severe non-compliance. For multicenter studies, this can occur at one or more or at all sites.
- If GSK determines such action is needed, GSK will discuss the reasons for taking such action with the investigator or the head of the medical institution (where applicable). When feasible, GSK will provide advance notification to the investigator or the head of the medical institution, where applicable, of the impending action.
- If the study is suspended or prematurely discontinued for safety reasons, GSK will promptly inform all investigators, heads of the medical institutions (where applicable) and/or institution(s) conducting the study. GSK will also promptly inform the relevant regulatory authorities of the suspension or premature discontinuation of the study and the reason(s) for the action.
- If required by applicable regulations, the investigator or the head of the medical institution (where applicable) must inform the IRB/IEC promptly and provide the reason for the suspension or premature discontinuation.

10.6. Records Retention

- Following closure of the study, the investigator or the head of the medical institution (where applicable) must maintain all site study records (except for those required by local regulations to be maintained elsewhere), in a safe and secure location.
- The records must be maintained to allow easy and timely retrieval, when needed (e.g., for a GSK audit or regulatory inspection) and must be available for review in conjunction with assessment of the facility, supporting systems, and relevant site staff.
- Where permitted by local laws/regulations or institutional policy, some or all of these records can be maintained in a format other than hard copy (e.g., microfiche, scanned, electronic); however, caution needs to be exercised before such action is taken.
- The investigator must ensure that all reproductions are legible and are a true and accurate copy of the original and meet accessibility and retrieval standards, including re-generating a hard copy, if required. Furthermore, the investigator must ensure there is an acceptable back-up of these reproductions and that an acceptable quality control process exists for making these reproductions.
- GSK will inform the investigator of the time period for retaining these records to comply with all applicable regulatory requirements. The minimum retention time will meet the strictest standard applicable to that site for the study, as dictated by any institutional requirements or local laws or regulations, GSK standards/procedures, and/or institutional requirements.

- The investigator must notify GSK of any changes in the archival arrangements, including, but not limited to, archival at an off-site facility or transfer of ownership of the records in the event the investigator is no longer associated with the site.

10.7. Provision of Study Results to Investigators, Posting of Information on Publicly Available Clinical Trials Registers and Publication

Where required by applicable regulatory requirements, an investigator signatory will be identified for the approval of the clinical study report. The investigator will be provided reasonable access to statistical tables, figures, and relevant reports and will have the opportunity to review the complete study results at a GSK site or other mutually-agreeable location.

GSK will also provide the investigator with the full summary of the study results. The investigator is encouraged to share the summary results with the study subjects, as appropriate.

The procedures and timing for public disclosure of the results summary and for development of a manuscript for publication will be in accordance with GSK Policy.

10.8. Review Committees

A PAC composed of independent specialists in gastroenterology will review cases of possible pancreatitis. Details of this committee and case adjudication will be described in a separate charter.

12. APPENDICES

12.1. Appendix 1 – Abbreviations and Trademarks

Abbreviations

AE	adverse event
ALT (SGPT)	alanine aminotransferase (serum glutamic pyruvic transaminase)
AST (SGOT)	aspartate aminotransferase (serum glutamic oxaloacetic transaminase)
BUN	blood urea nitrogen
CI	confidence interval
CPK	creatine phosphokinase
CV	cardiovascular
DNA	deoxyribonucleic acid
ECG	electrocardiogram
eCRF	electronic case report form
eGFR	estimated glomerular filtration rate
ELISA	enzyme-linked immunosorbent assay
EMA	European Medicines Agency
FDA	US Food and Drug Administration
FFA	free fatty acids
FPG	fasting plasma glucose
FRP	females of reproductive potential
FSH	follicle stimulating hormone
GCP	Good Clinical Practice
GGT	gamma glutamyl transferase
GI	gastrointestinal
GLP-1	glucagon-like peptide-1
GSK	GlaxoSmithKline
HA	human albumin
HbA1c	glycated hemoglobin
hCG	human chorionic gonadotrophin
HDL-c	high density lipoproteins
HRT	hormone replacement therapy
IB	Investigator's Brochure
ICH	International Conference on Harmonization
IEC	Independent Ethics Committee
INR	international normal range
IP	Investigational product
IRB	Institutional Review Board
ISRs	injection site reactions
ITT	intent-to-treat
LDH	lactate dehydrogenase
LDL-c	low density lipoproteins;

MACE	major adverse cardiovascular event
MCH	mean corpuscular hemoglobin
MCV	mean corpuscular volume
MDRD	Modification of Diet in Renal Disease
MedDRA	Medical Dictionary for Regulatory Activities
MEN-2	multiple endocrine neoplasia type 2
MI	myocardial infarction
MSDS	Material Safety Data Sheet
MTC	medullary thyroid cancer
PAC	Pancreatitis Adjudication Committee
PD	pharmacodynamics
PK	pharmacokinetics
OC RDC	Oracle Clinical Remote Data Capture
RAP	Reporting Analysis Plan
RBC	red blood cell
RNA	ribonucleic acid
s.c.	subcutaneous
SAE	serious adverse event
SmPC	Summary of Product Characteristics
SRM	Study Reference Manual
SU	sulfonylureas
T2DM	type 2 diabetes mellitus
ULN	upper limit of normal range
WBC	white blood cell
WCBP	women of child bearing potential

Trademark Information

Trademarks of the GlaxoSmithKline group of companies
NONE

Trademarks not owned by the GlaxoSmithKline group of companies
MedDRA
SpectrMAX

12.2. Appendix 2: GSK Modified List of Highly Effective Methods for Avoiding Pregnancy in Females of Reproductive Potential (FRP)

1. Contraceptive subdermal implant that meets effectiveness criteria including a <1% rate of failure per year, as stated in the product label.
2. Intrauterine device or intrauterine system that meets effectiveness criteria including a <1% rate of failure per year, as stated in the product label [Trussell, 2011]
3. Oral Contraceptive, either combined or progestogen alone [Trussell, 2011]
4. Injectable progestogen [Trussell, 2011]
5. Contraceptive vaginal ring [Trussell, 2011]
6. Percutaneous contraceptive patches [Trussell, 2011]
7. Male partner sterilization prior to the female subject's entry into the study, and this male is the sole partner for that subject. The information on the male sterility can come from interview with the subject on her male partner's medical history.
8. Male condom combined with a female diaphragm, with or without a vaginal spermicide (foam, gel, film, cream, or suppository).

These allowed methods of contraception have a failure rate of less than 1% per year but are only effective when used consistently, correctly and in accordance with the product label. The investigator is responsible for ensuring that subjects understand how to properly use these methods of contraception.

References

Trussell J, Contraceptive Efficacy. In: Hatcher RA, Trussell J, Nelson AL, Cates W, Kowal D, and Policar M (editors). Contraceptive Technology: Twentieth Revised Edition. New York: Ardent Media, 2011. Table 26-1

12.3. Appendix 3: Liver Safety Required Actions and Follow up Assessments

Phase III-IV liver chemistry stopping and increased monitoring criteria have been designed to assure subject safety and evaluate liver event etiology (in alignment with the FDA premarketing clinical liver safety guidance).

<http://www.fda.gov/downloads/Drugs/GuidanceComplianceRegulatoryInformation/Guidances/UCM174090.pdf>

Phase III-IV liver chemistry stopping criteria and required follow up assessments

Liver Chemistry Stopping Criteria - Liver Stopping Event	
ALT-absolute	ALT \geq 8xULN
ALT Increase	ALT \geq 5xULN but <8xULN persists for \geq 2 weeks ALT \geq 3xULN but <5xULN persists for \geq 4 weeks
Bilirubin^{1,2}	ALT \geq 3xULN and bilirubin \geq 2xULN (>35% direct bilirubin)
International Normal Range (INR)²	ALT \geq 3xULN and INR>1.5, if INR measured
Cannot Monitor	ALT \geq 5xULN but <8xULN and cannot be monitored weekly for \geq 2 weeks ALT \geq 3xULN but <5xULN and cannot be monitored weekly for \geq 4 weeks
Symptomatic³	ALT \geq 3xULN associated with symptoms (new or worsening) believed to be related to liver injury or hypersensitivity
Required Actions and Follow up Assessments following ANY Liver Stopping Event	
Actions	Follow Up Assessments

 Immediately discontinue study treatment Report the event to GSK within 24 hours Complete the liver event eCRF and complete an SAE data collection tool if the event also meets the criteria for an SAE² Perform liver event follow up assessments Monitor the subject until liver chemistries resolve, stabilize, or return to within baseline (see MONITORING below) Do not restart/rechallenge subject with 	
 Viral hepatitis serology⁴ Only in those with underlying chronic hepatitis B at study entry (identified by positive hepatitis B surface antigen) quantitative hepatitis B deoxyribonucleic acid (DNA) and hepatitis delta antibody⁵. Blood sample for PK analysis, obtained within 3 half-lives (15 days) after last dose⁶ Serum creatine phosphokinase (CPK) and lactate dehydrogenase (LDH). Fractionate bilirubin, if total


study treatment
 
 If restart/rechallenge not allowed or not granted, permanently discontinue study treatment and may continue subject in the study for any protocol specified follow up assessments 
MONITORING:
 
For bilirubin or INR criteria:
 
 Repeat liver chemistries (include ALT, AST, alkaline phosphatase, bilirubin) and perform liver event follow up assessments within 24 hrs Monitor subjects twice weekly until liver chemistries resolve, stabilize or return to within baseline A specialist or hepatology consultation is recommended 
For All other criteria:
 
 Repeat liver chemistries (include ALT, AST, alkaline phosphatase, bilirubin) and perform liver event follow up assessments within 24-72 hrs Monitor subjects weekly until liver chemistries resolve, stabilize or return to within baseline 	
bilirubin\geq2xULN
 
 Obtain complete blood count with differential to assess eosinophilia Record the appearance or worsening of clinical symptoms of liver injury, or hypersensitivity, on the AE report form Record use of concomitant medications on the concomitant medications report form including acetaminophen, herbal remedies, other over the counter medications. Record alcohol use on the liver event alcohol intake case report form 
For bilirubin or INR criteria:
 
 Anti-nuclear antibody, anti-smooth muscle antibody, Type 1 anti-liver kidney microsomal antibodies, and quantitative total immunoglobulin G (IgG or gamma globulins). Serum acetaminophen adduct HPLC assay (quantifies potential acetaminophen contribution to liver injury in subjects with definite or likely acetaminophen use in the preceding week [James, 2009]). NOTE: not required in China Liver imaging (ultrasound, magnetic resonance, or computerised tomography) and /or liver biopsy to evaluate liver disease: complete Liver Imaging and/or Liver Biopsy eCRF forms.
---	---

- Serum bilirubin fractionation should be performed if testing is available. If serum bilirubin fractionation is not immediately available, discontinue study treatment for that subject if ALT \geq 3xULN **and** bilirubin \geq 2xULN. Additionally, if serum bilirubin fractionation testing is unavailable, **record presence of detectable urinary bilirubin on dipstick**, indicating direct bilirubin elevations and suggesting liver injury.
- All events of ALT \geq 3xULN **and** bilirubin \geq 2xULN (>35% direct bilirubin) or ALT \geq 3xULN **and** INR>1.5, if INR measured which may indicate severe liver injury (possible 'Hy's Law'), **must be reported as an SAE (excluding studies of hepatic impairment or cirrhosis)**; INR measurement is not required and the threshold value stated will not apply to subjects receiving anticoagulants
- New or worsening symptoms believed to be related to liver injury (such as fatigue, nausea, vomiting, right upper quadrant pain or tenderness, or jaundice) or believed to be related to hypersensitivity (such as fever, rash or eosinophilia)
- Includes: Hepatitis A IgM antibody; Hepatitis B surface antigen and Hepatitis B Core Antibody (IgM); Hepatitis C ribonucleic acid (RNA); Cytomegalovirus IgM antibody; Epstein-Barr viral capsid antigen IgM antibody (or if unavailable, obtain heterophile antibody or monospot testing); Hepatitis E IgM antibody

5. If hepatitis delta antibody assay cannot be performed,, it can be replaced with a PCR of hepatitis D RNA virus (where needed) [Le Gal, 2005].
6. PK sample may not be required for subjects known to be receiving placebo or non-GSK comparator treatments. Record the date/time of the PK blood sample draw and the date/time of the last dose of study treatment prior to blood sample draw on the eCRF. If the date or time of the last dose is unclear, provide the subject's best approximation. If the date/time of the last dose cannot be approximated OR a PK sample cannot be collected in the time period indicated above, do not obtain a PK sample. Instructions for sample handling and shipping are in the SRM.

Phase III-IV liver chemistry increased monitoring criteria with continued therapy

Liver Chemistry Increased Monitoring Criteria – Liver Monitoring Event	
Criteria	Actions

ALT \geq5xULN and <8xULN and bilirubin <2xULN without symptoms believed to be related to liver injury or hypersensitivity, and who can be monitored weekly for 2 weeks.
 
OR
 
ALT \geq3xULN and <5xULN and bilirubin <2xULN without symptoms believed to be related to liver injury or hypersensitivity, and who can be monitored weekly for 4 weeks.
	
 • Notify the GSK medical monitor within 24 hours of learning of the abnormality to discuss subject safety. • Subject can continue study treatment • Subject must return weekly for repeat liver chemistries (ALT, AST, alkaline phosphatase, bilirubin) until they resolve, stabilise or return to within baseline • If at any time subject meets the liver chemistry stopping criteria, proceed as described above • If ALT decreases from ALT \geq5xULN and <8xULN to \geq3xULN but <5xULN, continue to monitor liver chemistries weekly. • If, after 4 weeks of monitoring, ALT <3xULN and bilirubin <2xULN, monitor subjects twice monthly until liver chemistries normalize or return to within baseline.

References

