5.4.1. Liver Chemistry Stopping Criteria

Liver chemistry stopping and increased monitoring criteria have been designed to assure subject safety and evaluate liver event etiology (in alignment with the FDA premarketing clinical liver safety guidance).

[figure not shown]
<http://www.fda.gov/downloads/Drugs/GuidanceComplianceRegulatoryInformation/Guidances/UCM174090.pdf>

Phase III-IV Liver Chemistry Stopping and Increased Monitoring Algorithm

Liver Safety Required Actions and Follow up Assessments Section can be found in [Appendix 3](#).

Phase III-IV Liver Chemistry Increased Monitoring Algorithm with Continued Therapy for ALT $\geq 3x$ upper limit of normal (ULN) but $< 8x$ ULN

Liver Safety Required Actions and Follow up Assessments Section can be found in [Appendix 3](#).

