5.4.1.1. Study Treatment Restart or Rechallenge

Study treatment restart or rechallenge after liver chemistry stopping criteria are met by any subject participating in this study is not allowed.

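### Read literally, Appendix 3 stops an ALT that rises past 5xULN late in the first four weeks later than one that stays at 4xULN

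*Protocol*

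**What the plan says.** Protocol Section 12.3 (Appendix 3) gives two ALT persistence criteria:

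- lower band: ALT at or above "3xULN but <5xULN persists for" at least 4 weeks;
- upper band: ALT at or above "5xULN but <8xULN persists for" at least 2 weeks.

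Other rows of the same table stop treatment for ALT of 8xULN or more, for raised bilirubin or INR with ALT of 3xULN or more, for symptoms with ALT of 3xULN or more, and for subjects who cannot be tested weekly. The action after any of these is "Immediately discontinue study treatment". Section 5.4 makes withdrawal mandatory, and Section 5.4.1.1 makes it permanent: "Study treatment restart or rechallenge after liver chemistry stopping criteria are met by any subject participating in this study is not allowed".

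Until a row is met, the increased-monitoring table in Appendix 3 applies to both bands. It requires weekly tests and says "Subject can continue study treatment". It gives one instruction for a move between bands, and only for a fall from the upper to the lower: "continue to monitor liver chemistries weekly". It also gives one step at a fixed time, which relaxes testing: "If, after 4 weeks of monitoring, ALT <3xULN and bilirubin <2xULN". It has no instruction for a rise from the lower to the upper band.

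**The concern.** The shorter period in the upper band shows that a higher ALT is meant to stop treatment sooner. Because the lower row ends at 5xULN, a literal reader takes a subject whose ALT passes 5xULN out of the 4-week row and starts a new 2-week count. If that happens late enough, the worsening subject stops after the stable one, which reverses the evident purpose of the rule.

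The cap is not forced by the table's format: the bilirubin, INR and symptom rows all use ALT of 3xULN or more with no upper bound.

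At stake is the timing of a permanent stop, and one or two further weekly 50 mg doses while ALT is rising. Section 4.6.1 lists hepatotoxicity as a potential risk and relies on these withdrawal criteria as mitigation. Sites that count differently would also stop subjects with identical readings at different times.

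**Working it through.** **Inputs.** From Appendix 3: lower band 3 to <5xULN, stop after 4 weeks; upper band 5 to <8xULN, stop after 2 weeks; weekly tests during monitoring. Week 0 is the first reading at or above 3xULN. No other stopping row is met.

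**Rules compared.** Let *r* be the week at which ALT is first seen in the upper band, where it then stays.

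- Literal: each clock runs only while ALT is inside its own band. For *r* ≤ 4, stop week = *r* + 2.
- Uncapped (ALT ≥3xULN for at least 4 weeks, or ≥5xULN for at least 2 weeks): stop week = the smaller of 4 and *r* + 2.

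**The plan's own figures.** Steady 4xULN stops at week 4 and steady 6xULN at week 2, matching the two rows.

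**Elapsed-time count** (4 weeks between the first and last reading in the band):

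| ALT course | Literal | Uncapped | Delay (weeks) |
|---|---|---|---|
| Steady 4xULN | 4 | 4 | 0 |
| Rise first seen week 1 | 1 + 2 = 3 | 3 | 0 |
| Week 2 | 2 + 2 = 4 | 4 | 0 |
| Week 3 | 3 + 2 = 5 | 4 | 1 |
| Week 4 | 4 + 2 = 6 | 4 | 2 |
| Week 5 or later | 4 (already stopped) | 4 | 0 |

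In continuous time the delay is *r* − 2 weeks for a rise after week 2 and up to week 4. A rise at week 2.5, for example, stops at 4.5 instead of 4. On weekly tests the delay is 1 or 2 weeks, hence 1 or 2 further weekly doses.

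**Reading count** (each reading is one week, so 4 readings in the lower band or 2 in the upper):

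- Steady lower band: stop at the 4th reading under both rules.
- Rise at the 2nd reading: stop at the 3rd under both.
- Rise at the 3rd reading: stop at the 4th under both.
- Rise at the 4th reading: literal stop at the 5th, uncapped at the 4th, a delay of one week.

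The reversal therefore appears under both conventions, but its window and size depend on which one a site uses. The visible text does not define how persistence is counted.

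**The case against.** **The algorithm cannot be seen.** Section 5.4 points to Section 5.4.1, whose figure is not visible. Its surviving heading, "Increased Monitoring Algorithm with Continued Therapy for ALT", covers 3xULN to <8xULN as one pathway, which fits a single running clock. This limits confidence but does not remove the point. If the figure repeats the capped rows, the problem stands; if it does not, Appendix 3 disagrees with it and still needs correcting.

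**An uncapped rule was probably intended.** After 4 weeks of monitoring, less frequent testing is offered only below 3xULN, and nothing says that the clock restarts when ALT worsens. This stands as evidence of intent. The printed rows do not say it, and a rule meant to be automatic should not depend on inference.

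**Other safeguards apply.** The medical monitor must be told within 24 hours, testing is weekly, and an investigator who sees a safety concern must withdraw the subject. These reduce the harm. They rest on judgement, which the numerical row is there to make unnecessary.

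**A stronger reading does not hold.** A reader might infer that an ALT crossing 5xULN and returning could postpone the stop much further, or indefinitely. The documents do not support relying on this: each such sequence contains a fall from the upper to the lower band, and Appendix 3 deals with that fall by continued weekly testing.

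**Conclusion.** The point holds as a minor drafting fault, with moderate confidence. On a literal reading of Appendix 3, a sustained rise from 3 to <5xULN into 5 to <8xULN, first seen at week 3 or 4, delays the mandatory stop by 1 or 2 weeks on an elapsed-time count. On a reading count the delay is one week, for a rise at the fourth reading only.

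This rests on the literal reading and on no other stopping row being met: the subject has no symptoms, attends weekly, and has bilirubin <2xULN and ALT <8xULN. Rises first seen by week 2 are not delayed, and rises after week 4 come after the stop. The protocol gives no rate for such courses; few subjects are likely to be affected. No endpoint, sample size or analysis changes.

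It should not be inferred that the 1-to-2-week figure applies however weeks are counted, or that the thresholds and durations are themselves wrong.

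**What to change.** At the next amendment:

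1. Word the 4-week criterion as ALT ≥3xULN persisting for at least 4 weeks, deleting the <5xULN bound. Keep ALT ≥5xULN for at least 2 weeks. The <8xULN bound on that row does no harm, since 8xULN or more stops treatment at once.
2. Align the monitoring table and the Section 5.4.1 algorithm with this wording.
3. In the monitoring-table bullet on a fall from the upper to the lower band, state whether a subject whose ALT has fallen and stays there starts a new 4-week count.

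Step 3 belongs with step 1. Deleting the bound alone would also bring forward the stop for some improving subjects. With ALT in the upper band at week 0 and fallen by week 1 or 2, the literal stop is 1 + 4 = week 5 or 2 + 4 = week 6, and the uncapped stop is week 4, with no restart.

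No tests are added, because weekly testing is already required. The cost is that a few subjects stop permanently 1 to 2 weeks earlier.
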